46    relationship to emotional well-being and functional communication, treatment that  
47    improves naming deficits will positively influence quality of life in many of these individuals.  
48    The approach taken to remediate naming deficits in aphasia is to treat impaired WM systems

1 on the premise that certain cognitive processes underlie linguistic functions in aphasia. This  
2 approach represents a departure from most behavioral-based naming treatment approaches,  
3 but reflects a growing recognition that WM systems in individuals with aphasia impact  
4 linguistic performance . The addition of a-tDCS as a neuromodulation tool to increase  
5 cortical excitability (upregulate) the working memory center to target naming is a novel  
6 approach in aphasia. These findings, , will provide valuable information regarding the role  
7 WM plays in naming and the potential benefit of using neuromodulation to the DLPFC to  
8 influence naming in aphasia.

9

- 10 • **Is the design of the study appropriate for the questions that are posed?**

11

12 *Treatment Design:*

13 A single subject cross-over design with a 4 week wash out period will be used. Two treatment  
14 conditions will be presented. The sham (SHAM) condition will consist of presentation of sham  
15 tDCS for 20 minutes followed by behavioral naming treatment. The real treatment condition  
16 (REAL) will consist of 20 minutes of a-tDCS to the left DLPFC followed by behavioral naming  
17 treatment. The length of behavioral naming treatment will depend on how long each participant  
18 takes to go through the treatment stimuli twice. A SHAM-REAL sequence will be used across all  
19 participants. Although order effects may be introduced using the same sequence across  
20 participants, the small number of participants makes it difficult to interpret any data that comes  
21 from using a counterbalanced presentation of treatment.

22 Treatment will be provided over five consecutive days. A minimum of a one-month washout  
23 period will be provided between the two conditions (Figure 1). Prior to initiating the REAL  
24 treatment condition, the naming RTs obtained on the second word list during the pre-treatment  
25 testing period (prior to the initiation of the SHAM condition) will be compared to the naming RTs  
26 obtained after the washout period. RTs will be analyzed to ensure that no lasting treatment  

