27 effects remain after the SHAM condition. If performance on naming RTs is +/- 1 standard  
28 deviation from the individual's benchmark mean, the REAL treatment condition will begin. If  
29 performance on naming RTs is > +/- 1 standard deviation from the individual's benchmark  
30 mean, REAL treatment will be postponed until the mean RTs fall within +/- 1 standard deviation  
31 of the benchmark. Periodic checks will be conducted weekly to identify when to begin REAL  
32 condition. Once there are minimal differences between naming RTs on the second word list,  
33 the REAL treatment will be initiated.

34

[figure not shown]
35 *Outcome measures:*

36 Two different word lists will be generated; a different list will be used for each treatment  
37 condition to control for exposure and learning effect. Pretreatment testing outcome measures will  
38 be recorded for 5 consecutive days for each outcome measure including: 1) naming accuracy 2)  
39 naming RTs on both word lists 3) performance on motor speech tasks and 4) performance on  
40 working memory tasks. Stability of baseline performance, defined as no more than 20%  
41 difference between scores, will be obtained in five consecutive sessions. In addition, outcome  
42 measures will be obtained immediately after each treatment session. Five maintenance  
43 outcome measures will also be obtained upon completion of treatment. These sessions will take  
44 place at the Clinical Translational Science Institute (CTSI) on [name] on the University  
45 of MN campus. An adverse events questionnaire will also be given after each treatment session  
46 as a mechanism of participants reporting any discomfort.

47  
48  
49

50

1 **Figure 1. Treatment Schedule**

6 *tDCS Protocol.*

7 Treatment sessions will take place at the University of MN Clinical Translational Science  
8 Institute. Each participant will be seated comfortably in a chair. A swim cap will be placed on  
9 the participant's head to identify cranial landmarks for accurate electrode placement. The area  
10 referred to as F3 by the International 10/20 system for electroencephalogram electrode  
11 placement has been established as the optimal location for targeting the left DLPFC.  
12 The F3 region will be located by marking the vertex (the midpoint between left and right tragus  
13 and midpoint between nasion and inion), measuring the head circumference. When these  

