Picture + Cue Presentation	If the participant is unable to provide the name, the cues will be read, or if he/she is unable to read spontaneously, he/she will be asked to repeat after the clinician. If she/he is still unable to provide the picture name after the cue review, it will be provided.
Picture + Cue Review	Once the cues and picture are laid out on the table, the clinician will read each cue and name the picture. The participant will be encouraged to read/repeat with the clinician.

1  
2     • **Have the validity and reliability of measures been established or are there**  
3     **methods proposed for establishing validity and reliability?**

4  
5     Approximately 20% of each of the participant's behavioral treatment sessions will be  
6     observed by the co-investigator in order to obtain procedural integrity. Steps of the treatment  
7     protocol will be scored using a binary (+/-) coding system. Point-by-point agreement will be  
8     obtained. Reliability in scoring naming error types will also be obtained using a table that  
9     lists the most common aphasic naming errors, definitions and examples of each error type.  
10    Point-by-point agreement will be obtained.

11  
12     • **Is the proposed subject population appropriate?**

13     Participants will be recruited via emails sent to Twin Cities metro area hospital and  
14     aphasia/stroke support groups. Potential participants will then be screened for eligibility for  
15     the study.

16     **Screening.** Potential participants will be seen for 2-3 sessions to undergo comprehensive  
17     cognitive-linguistic assessment to determine eligibility for the study. This assessment will  
18     take place within the participant's home to provide a comfortable, natural environment for the  
19     potential participant. Behavioral assessment measures will include the Western Aphasia  
20     Battery (WAB) which will be used to obtain overall language function via the WAB Aphasia  
21     Quotient (WAB AQ), the Boston Naming Test (BNT) in order to obtain naming function,,  
22     Apraxia Battery for Adults (ABA-2) in order to determine apraxia of speech severity, and  
23     working memory tasks to determine subvocal rehearsal processes and phonological short-  
24     term store abilities.

25     These participants must meet the following inclusionary criteria:

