26         • a diagnosis of moderate-moderately severe non-fluent aphasia based on  
27         performance on the WAB (see above screening procedures).  
28         • a diagnosis of moderate-moderately severe non-fluent aphasia based on  
29         performance on the BNT (see above screening procedures).  
30         • a diagnosis of mild-moderate apraxia of speech (AoS) based on performance on the  
31         ABA-2 (see above screening procedures).  
32         • completion of high school or GED  
33         • normal or corrected-to-normal vision  
34         • adequate hearing acuity for 1:1 conversational exchanges  
35         • use of English as primary language  
36         • a vascular lesion in the dominant left hemisphere, not in the region of the DLPFC  
37         verified by an MRI scan within six months of the start of the study.

38     These participants must also meet the following exclusionary criteria:

39  
40         • no previous history of neurological- or psychiatric-based illnesses or disease,  
41         language or learning disabilities, or alcohol/substance abuse  
42         • no history of seizures  
43         • no metal implants in the head (except dental fillings)  
44         • no lesion in the left DLPFC confirmed by MRI

1       • no current pregnancy

2  
3 Individuals who meet the inclusionary/exclusionary criteria and who are still interested in  
4 participating will then be consented to participate in the research study. After four  
5 participants have been identified as eligible and consented for the study, recruitment will  
6 stop.

7       • **Are statistical considerations, including sample size and justification, estimated  
8 accrual and duration, and statistical analysis clearly described and adequate to  
9 meet the study objectives?**

10  
11 Descriptive statistics such as naming percent accuracy, range of naming percent accuracy,  
12 number of cues generated independently, and rates of naming errors, will be collected. Although  
13 normally distributed data is not expected in this small sample size and in this population of  
14 participants, a Shapiro-Wilk test of normal distribution will be conducted to report the  
15 distribution. Single subject analysis techniques will be used such as visual inspection, graphical  
16 analysis and confidence interval comparison.

17  
18 *Aim 1.* To address the feasibility and safety aim, the number and type of adverse events for  

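### Outside speech-language therapy and home naming practice are neither limited nor recorded, and the fixed SHAM-then-REAL order lets them be mistaken for an effect of REAL

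*Combined protocol and SAP*

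**What the plan says.** All references are to the combined protocol and SAP.

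- **Treatment Design.** "A single subject cross-over design with a 4 week wash out period will be used". A few lines later the interval is put differently, beside the length of each block: "Treatment will be provided over five consecutive days. A minimum of a one-month washout" period. The order is fixed: "A SHAM-REAL sequence will be used across all" participants. The plan admits that a single order may introduce order effects.
- **Check before REAL (same subsection).** List 2 naming RTs after the washout are compared with those taken before SHAM. REAL waits, with weekly re-checks, until they lie within one SD of the participant's own pre-SHAM mean.
- **Outcome measures.** Accuracy, RT on both lists, motor speech and working memory are measured on five consecutive days before treatment, after every treatment session, and five times afterwards. The only participant questionnaire described concerns adverse events.
- **Stimuli.** Forty untreated pictures are shown at baseline and after treatment, to judge both treatment and generalization effects.
- **Subject population.** "Participants will be recruited via emails sent to Twin Cities metro area hospital and" aphasia or stroke support groups. The criteria cover education, vision, hearing, imaging, implants, pregnancy and items such as "no previous history of neurological- or psychiatric-based illnesses or disease". None concerns current therapy.
- **Statistical considerations.** Recruitment stops at four participants. Each is read individually by means with 95% confidence intervals, visual inspection and, for accuracy, a d statistic.

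**The concern.** Hypothesis 2 expects improvement after REAL but not after SHAM, judged within each person. Outside naming or cognitive therapy, or practice at home, can act on the same outcomes. Because the order never varies, the washout always falls before REAL and never before SHAM. There is no reversed sequence or parallel group in which such an influence could average out, and four participants would be too few for that in any case.

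Therapy that continues or begins during the washout could look like a benefit of REAL. Therapy that stops could hide one. Without a record, the analyst cannot tell these cases from a stimulation effect, and the information may not be recoverable afterwards. Aim 2 is also meant to supply a sample size for later work, so a misattributed change would carry forward.

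**Working it through.** The plan states no power, assumed effect or outside-therapy rate, so there is no figure of its own to reproduce. The check has four parts.

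**1. Calendar.** Inputs from the text: 5 baseline days, 5 SHAM days, a 28-day washout, 5 REAL days. Assumptions: blocks run back to back, and the pre-SHAM baseline is the reference for both conditions.
- Baseline is days 1-5 (midpoint 3), SHAM days 6-10 (midpoint 8), washout days 11-38, REAL days 39-43 (midpoint 41).
- Baseline to SHAM: 8 - 3 = 5 days. Baseline to REAL: 41 - 3 = 38 days.
- With five maintenance days before the washout and a 31-day month: 38 + 5 + 3 = 46 days. A postponement of REAL adds more.
- If each condition had its own adjacent five-day baseline, both intervals would be 5 days and the contrast would disappear.

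**2. Illustrative hours.** Outside hours = days / 7 x weekly rate, with an assumed 1-3 hours a week.
- Before SHAM: 5/7 x 1 to 3 = 0.7-2.1 hours.
- Before REAL: 38/7 x 1 to 3 = 5.4-16.3 hours.
- Study therapy per block: 20 items x 2 passes x 5 days at an assumed 36-100 seconds per pass. 40 x 36 x 5 / 3600 = 2.0 hours; 40 x 100 x 5 / 3600 = 5.6 hours.
- The upper value is not a ceiling. Table 1's ten-second windows alone allow 10 + 30 + 10 + 30 = 80 seconds before repetition, the second naming attempt and review.

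**3. What the RT check lets through.** Simulation of 400,000 runs, assuming normal, independent session means, a benchmark mean and SD from the five baseline sessions, and one session per check.

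| True RT drift (session SDs) | Passes first check | Passes at least one of five weekly checks |
|---|---|---|
| 0 | 59% | 96% |
| 1 | 43% | 87% |
| 2 | 17% | 53% |
| 3 | 4% | 15% |

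The check tends to stop large RT drift and often passes drift of about one SD. The text does not say whether the SD is taken over sessions or items; the session SD is assumed here.

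**4. Accuracy, which has no such check.** d = gain / baseline SD, and the plan's small benchmark is 4.0. The smallest non-zero SD for five whole-number scores (for example 10, 10, 10, 10, 11) is 0.45. If the 20% stability rule means 4 items of 20, the largest (8, 8, 8, 12, 12) is 2.19. A carried-in gain of 4.0 x 0.45 = 1.8 items to 4.0 x 2.19 = 8.8 items would then reach the small benchmark.

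**The case against.** The plan is not without protection. The RT check limits carried-in change on list 2 from any source, outside therapy included. A general naming gain should also appear on the 40 untreated pictures, which belong to the primary outcomes. Both points stand, but only in part. The RT check covers one of four outcome domains, and an untreated-list gain may be read as generalization. Neither covers working memory or motor speech.

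The 5-versus-38-day contrast depends on the reference baseline. The text describes only a pre-SHAM baseline, but never says that REAL is measured against it for accuracy, working memory and motor speech, and Figure 1 (the schedule) is not shown. A second baseline there would remove most of the accumulated difference. It would not reveal therapy that starts, stops or changes between or during the blocks.

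A reader might infer that outside therapy is in fact being credited to REAL, or that it outweighs the study's own therapy. The documents support neither. They give no rate of outside therapy, and the recruitment route makes it plausible without showing it. Hours are not bias: nothing suggests that outside therapy would train the 20 list 2 pictures.

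Finally, this is a four-person feasibility study that already discloses order effects. That limits the weight of the point. The disclosure does not name outside therapy, and it collects no data on it.

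**Conclusion.** The concern holds in a limited form. In the available text, outside therapy and home practice are neither limited nor recorded. With a fixed order, a washout of at least four weeks before REAL only, and no stated repeat measurement before REAL except list 2 RT, their influence cannot be separated from that of REAL. It could run in either direction.

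The size is unknown. The hours above show scale under assumed rates and an assumed reference baseline; the RT pass rates rest on the simulation's assumptions. None is an estimate of bias. The point bears on how Aim 2 can be interpreted and does not affect Aim 1. The remedy is a cheap improvement that must be in place before the first baseline day.

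**What to change.** **Outcome measures.**
- Add a short log of dates, minutes and type of any other speech-language or cognitive therapy and home naming practice. Complete it at each baseline, treatment and maintenance visit, at the post-washout RT check (covering the washout by recall), and at any weekly re-check. Weekly checks are described only when REAL is postponed, so the log cannot count on contacts during the initial washout.
- At the pre-REAL RT check, also record accuracy, working memory, motor speech and the control list. Show REAL change against these values as well as against the pre-SHAM baseline. This addresses steady outside therapy, which a log alone does not. The sentence confining the control list to baseline and post-treatment testing needs a matching edit.

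**Statistical considerations.**
- Report cumulative outside minutes before and during each block beside each participant's result.
- State in advance that a REAL-SHAM difference is flagged as confounded in a participant whose outside therapy started, stopped or changed between the blocks. Show Aim 2 with and without such participants.

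The two statements of washout length should also be reconciled.

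**Cost.** A few minutes per visit, one longer pre-REAL visit and imperfect recall over the washout. One participant's result may have to be reported as uninterpretable. The log restricts nobody's care.

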30   Two conditions: 1)a-tDCS (2mA for 20 minutes) will be applied over the left DLPFC followed  
31   immediately by behavioral naming therapy and 2) sham tDCS followed immediately by  
32   behavioral naming therapy will be presented to participants with non-fluent aphasia. *Hypothesis*  
33   1: no adverse events will be reported during or following this treatment and all participants will  
34   complete the study.  
35

36   **Aim 2:** *Identify effectiveness of a-tDCS to the left DLPFC combined with behavioral naming*  
37   *treatment in Broca's aphasia and establish a sample size for future investigations of this nature.*  
38   A small sample size will be used in this study to investigate effectiveness of the use of a-tDCS  
39   to the left DLPFC with behavioral therapy to target naming in non-fluent aphasia. *Hypothesis 2:*  
40   Improvements in working memory, naming reaction time and naming accuracy will be observed  
41   after the real a-tDCS condition but not after the sham a-tDCS condition.  
42

1     • **Is the primary outcome (and secondary outcomes, as appropriate) clearly  
2     defined?**

3     Primary outcomes include: naming accuracy on treated and control items, naming RTs on  
4     treated and control items, performance on WM tasks, and motor speech tasks.

5     • **Are there adequate preliminary data in the literature (or from the investigator) to  
6     justify the proposed research? Has an adequate literature review been done to  
7     support this study?**

8  
9     WM systems are short-term, temporary stores that are activated when active manipulation of  
10    items is necessary. It could be argued that all linguistic tasks invoke WM systems since the  
11    execution of any linguistic task requires the ability to maintain activation of a representation until  
12    the targeted linguistic process is complete. Indeed, the close relationship between language  
13    and WM is represented in many WM models. Over the past few decades, there has been  
14    increasing recognition that aphasia is frequently accompanied by deficits in WM systems.  
15    Furthermore, such deficits adversely impact linguistic performance in aphasia. Accordingly,  
16    treatment protocols are being developed on the premise that treatments aimed at improving WM  
17    systems will improve linguistic function in aphasia. While a variety of WM treatment  

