5 and word length. Familiarity ratings will be obtained from a normative database. Visual  
6 complexity ratings will be also obtained from a group of 20 individuals using the instructions and  
7 rating scales as reported in Snodgrass and Vanderwart's article. The CELEX database, will  
8 be consulted to determine lexical frequency of the words (cues) used in the study. An additional  
9 40 pictures will be selected for a control (untreated) list that will be used only during baseline  
10 and post-treatment testing. Performance on treated and untreated lists will be compared to  
11 determine treatment effects and possible generalization effects.

12  
13 *Naming Treatment Procedures.* All participants will be provided the same protocol, which will  
14 highlight the process of rehearsing the cues associated with the picture name. Treatment  
15 sessions will last until each participant has gone through the treated items twice. To insure  
16 control during the protocol, a graduate student trained in the protocol will administer the  
17 treatment steps. She will be blinded to the objectives of the study and conditions that are being  
18 administered. Treatment sessions will be video recorded for reliability purposes. To insure that  
19 she is not aware of when tDCS is being administered, a screen will be in place between the  
20 tDCS machine and the treatment table. The protocol is provided in Table 1.

21  
22 **Table 1. Naming Treatment Protocol.**

Steps Involved in Naming Treatment Protocol	
Picture Presentation	Participant will be asked to name the picture. If she/he is unable to provide the name within 10 seconds, the name will be provided.
Cue Presentation	Cues that accompany the picture will be presented. He/she will be asked to read each cue word as it is presented. If he/she is unable to read the word spontaneously within 10 seconds, he/she will be asked to repeat each word after the clinician.
Cue Rehearsal	Both picture and cues are taken away. Participant is asked to rehearse the cue words silently for 10 seconds.
Cue Self-Generation	Participant will be asked to generate all three cues. For each instance that the participant is unable to provide a cue within 10 seconds, the cues will be provided. Once the cues have been provided, the participant will then be asked to provide the picture name.

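### A pass on the weekly ±1 SD check of list-2 reaction time does not show that effects of the SHAM block have gone

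*Combined protocol and SAP*

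**What the plan says.** The Treatment Design section of the combined protocol and SAP gives all participants SHAM first and REAL second, with at least a one-month washout. List-2 RTs from pre-treatment testing are then compared with list-2 RTs after the washout, and the purpose is explicit: "RTs will be analyzed to ensure that no lasting treatment" effects remain after SHAM. If RT is within ±1 SD of the individual's benchmark mean, REAL begins. If RT is further than that from the benchmark "mean, REAL treatment will be postponed until the mean RTs fall within +/- 1 standard deviation". The re-check rule reads "of the benchmark. Periodic checks will be conducted weekly to identify when to begin REAL", with no maximum number. A second wording of the pass criterion follows, without a figure: "Once there are minimal differences between naming RTs on the second word list".

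The text does not say whether the SD is between session means or between single namings, or how many sessions make a check.

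Other relevant provisions:
- The primary outcomes are naming accuracy and RT on "treated and control items, performance on WM tasks, and motor speech tasks".
- Outcome measures specifies five consecutive pre-treatment days, a 20% stability rule over five sessions, and a different word list for each condition.
- Recruitment stops at four participants.
- The Aim 2 analysis plots means and 95% confidence intervals for each participant. It does not say what REAL changes are measured from.
- The treatment schedule (Figure 1) is not shown in the text available.

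**The concern.** Hypothesis 2 expects improvement after REAL and not after SHAM. Both conditions deliver the same cue-rehearsal naming therapy and SHAM always comes first, so any gain kept from the first block matters for the comparison. The plan relies on this check to rule that out. A report that follows the text would say that washout was confirmed in each participant.

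Three features prevent a pass from supporting that statement.
1. Accuracy, control items, working memory and motor speech are primary outcomes and are not checked.
2. The check repeats until passed, so for a shift that persists, each further look can only raise the chance of a pass.
3. Being within 1 SD is a failure to see a large difference. It is not evidence of a small one.

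With four participants judged one by one, a retained gain credited to stimulation in even one of them would affect the conclusion. Aim 2 is also meant to inform the sample size of later studies.

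**Working it through.** The plan gives no error rate for the check, so there is no figure to reproduce. The calculation below is the pass probability of the rule as written.

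**Inputs from the protocol.** Benchmark of five sessions; limit ±1 SD; weekly repeats; 20 items per list; 20% stability rule.

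**Assumptions.** Normal data; independent checks; a true shift of d SD that does not fade; one or five sessions per check; four checks where repetition is shown. None of these is in the documents.

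**Session-mean SD, first check.** Let m and s be the mean and sample SD of the five benchmark sessions, and let the check average k sessions. A pass means |check − m| ≤ s. The probability is P(|T| ≤ 1/v), where v = √(1/5 + 1/k) and T is noncentral t with 4 df and noncentrality d/v. For k = 1, v = √1.2 and 1/v = 0.913. For k = 5, v = √0.4 and 1/v = 1.581.

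| True shift | First check, k = 1 | First check, k = 5 | By four checks, k = 1 | By four checks, k = 5 |
|---|---|---|---|---|
| 0 | 59% | 81% | 94% | 97% |
| 0.5 SD | 54% | 71% | 91% | 92% |
| 1 SD | 43% | 46% | 83% | 73% |
| 1.5 SD | 30% | 22% | 67% | 43% |
| 3 SD | 4% | 0.2% | 13% | 1% |

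The four-check columns are simulated (400,000 runs). With a week-to-week correlation of 0.8, the 1.5-SD figures by four checks fall to 49% and 32%.

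**What a pass tells us.** The likelihood ratio of a first-check pass for no shift against a 0.5-SD shift is 0.587/0.544 = 1.08 with one session and 0.811/0.707 = 1.15 with five. Both are close to 1. A failure is also weak evidence: with no carry-over, 41% (k = 1) or 19% (k = 5) of first checks fail.

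**Precision.** The 90% CI half-width for the shift is t(0.95, 4) × √1.2 = 2.34 SD with one session and t(0.95, 8) × √0.4 = 1.18 SD with five sessions, pooling the SD. Both exceed the 1-SD limit.

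**Item-level SD.** Take a check of 20 namings against a benchmark of 5 × 20 = 100, with known SD and independent items. The standard error is √(1/20 + 1/100) = 0.245 item-SD. A 0.5 item-SD shift passes the first check with probability Φ(0.5/0.245) − Φ(−1.5/0.245) = 98%. With the SD estimated, 10 to 20 usable RTs, and 0 to 30% of variance between sessions (assumed), the range is 74–97% for a one-session check. On this reading the check can be precise, but 1 SD is a wide margin.

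**Stability rule.** Suppose the 20% rule applies to list-2 RT as range divided by mean. The largest sample SD of five values with range R is √0.3 × R = 0.548R, so the session SD is at most 0.548 × 20% ≈ 11% of mean RT. Keeping only baselines that satisfy the rule, a 1.5-SD gain (faster RT) passes as follows:
- session CV 10% (assumed): 17% (k = 1) or 7% (k = 5) at the first check, and 49% or 19% by four checks;
- session CV 5% (assumed): 28% or 20%, and 66% or 41%, close to the table.

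At CV 10% the rule also raises first-check failures with no carry-over to 58% or 35%.

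**The case against.** The defence has real substance.

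- **List 2 is untrained in SHAM.** Separate lists are there to control exposure and learning, so only generalised or test-practice gain can reach list 2. This stands and limits how large a shift is plausible.
- **The stability rule may bound the tolerated gap.** On the range/mean reading it does so in absolute terms and lowers the pass rates. This stands for the session-SD reading. It does not rescue the item-level reading.
- **Waiting helps if carry-over fades.** A later pass may then partly reflect true washout. This stands, but a pass cannot distinguish fading from chance.
- **This is a go/no-go screen in a feasibility study of four people, not an equivalence test.** That is fair for its role as a screen. However, the plan itself claims that the check ensures no lasting effect, and that claim is what fails.
- **Order effects are already acknowledged.** That admission concerns the fixed sequence. The claim that carry-over is excluded is made separately.

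A reader might infer that the REAL results are shown to be biased. The documents do not support this. If REAL change in list-2 RT were measured from the check that passed, then for a persisting 1.5-SD gain passed at the first check, that check would misstate the true level by 0.92 session SD (k = 1) or 0.37 (k = 5), in REAL's favour. If it were measured from the pre-SHAM baseline, retained gain would count towards REAL. No section states either choice, and Figure 1 may contain a second baseline, so these are conditional scenarios only. Nor can one infer that the plan has no post-washout baseline.

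**Conclusion.** The point holds in a limited form. A pass describes list-2 RT on the day. It does not establish that SHAM-block effects have gone, either for that outcome or for the unchecked primary outcomes. The coverage gap and the absence of a limit on repeats follow from the text and need no calculation. On the session-SD reading a pass is almost as likely with a 0.5-SD shift as with none. On the item-level reading a 0.5-SD shift nearly always or usually passes.

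It would go too far to call the check useless, since a 3-SD gain rarely passes the first check on the session-SD reading. The cumulative figures rest on the assumed four checks, independence and a constant shift. Confidence is high on what a pass can show and moderate on the REAL baseline, which depends on a schedule that is not visible. The matter should be fixed because it changes what the trial may conclude.

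**What to change.** 1. In Treatment Design, replace the claim to ensure absence of lasting effects with a statement that the check describes list-2 RT only and is not evidence of washout. Reconcile the ±1 SD wording with the unquantified second wording.
2. State which SD is used and how many sessions make a check.
3. For each participant, report the list-2 RT difference, first scheduled post-washout assessment minus pre-SHAM, with its confidence interval, whether or not the check passed. Also report the number of checks needed.
4. Record naming accuracy, working memory and motor speech at that same first visit and report the same differences.
5. In the Aim 2 analysis, state that REAL changes are measured from post-washout data, using that first scheduled assessment rather than whichever check passed. If Figure 1 already shows a second baseline, use that.

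**Cost.** Items 1 to 3 are wording and reporting of data already planned. Item 4 means a longer visit for four participants. Control pictures can be added only if the visit counts as baseline, because the Stimuli section specifies "40 pictures will be selected for a control (untreated) list that will be used only during baseline" and post-treatment testing; their exposure would rise. For a postponed participant, the first assessment is at least a week older than the start of REAL. If carry-over fades meanwhile, it would tend to understate REAL's gain. A separate five-session baseline after the pass would be a larger schedule change and is not needed for this point.

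None of this removes the order effect of the fixed SHAM-REAL sequence, and no rule for when REAL starts is proposed.
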